Study Objectives	
 1. To determine the prevalence of underdiagnosis and undertreatment of common cardiometabolic conditions (i.e., hypertension, dyslipidemia, diabetes) in survivors of childhood cancer at high-risk of future serious cardiovascular disease. 2. Among survivors who are found to be underdiagnosed or undertreated, to determine (via randomized clinical trial) the efficacy of a counseling/educational intervention to improve control of these cardiometabolic conditions. 3. Determine barriers on among survivors enrolled on the randomized trial and their primary healthcare providers that contribute to undertreatment of the study's targeted cardiometabolic conditions.
Study Design	Aim 1 is an observational study. Aims 2 and 3 are based on a randomized clinical trial design.
Population	Participants in the existing Childhood Cancer Survivor Study cohort who are classified as high-risk for future cardiovascular disease based on their demographic and cancer therapy exposures.
Primary Endpoints	Aim 1: Prevalence of underdiagnosis and undertreatment of hypertension, dyslipidemia, and diabetes. Aim 2: Probability of having an undertreated condition
Secondary Endpoints	Aim 3: Determine whether intervention and control arms differ in terms of survivor knowledge, self-efficacy, and medication adherence, as well as differences in their providers' knowledge and self-efficacy related to the care of childhood cancer survivors.
Type of control	Delayed intervention control (i.e., can choose to receive the intervention at the end of the study period).
Trial Blinding	Study staff performing home visits and study statisticians will be blinded. Participants and study staff delivering the counseling intervention cannot be blinded given the nature of the study.
Treatment Groups	Group A: upfront intervention group (30 minute counseling session focused on survivorship care plan, personalized action plan; 15 minute booster session at 4 months) Group B: delayed intervention control group (30 minute counseling session focused on survivorship care plan, personalized action plan)
Treatment Schedule	Baseline: educational materials (survivorship care plan, personalized action plan, and 30 minute counseling intervention 4 months: 15 minute booster session
Efficacy Assessments	Baseline: patient questionnaire and 1 st home visit 4 months: action plan scoring by study staff 12 months: patient questionnaire and 2 nd home visit
No. subjects	Anticipate 800 for Aim 1, and project that ~480 maybe eligible to participate on Aims 2 and 3.
Estimated duration	5-years
Duration of Participation	1-year interval between initial survey and home visit and follow-up survey and home visit.

Table of Contents

1.0	GENERAL INFORMATION	5
2.0	INTRODUCTION.....	5
2.1	Introduction	5
2.2	Clinical Data to Date	8
2.3	Risks/Benefits	10
3.0	OVERVIEW OF CLINICAL TRIAL.....	11
3.1	Study Objectives	11
3.2	Study Population.....	12
3.3	Study Design	12
3.4	Estimated Accrual	13
3.5	Sponsor/Funding Source.....	13
4.0	SAFETY CONSIDERATIONS.....	13
5.0	SUBJECT ELIGIBILITY.....	14
5.1	Inclusion Criteria.....	14
5.2	Exclusion Criteria, applicable to all participants	15
6.0	SUBJECT RECRUITMENT & REGISTRATION	15
6.1	Recruitment	15
6.2	Registration.....	16
7.0	TREATMENT PLAN.....	17
7.1	Treatment Plan Overview	17
7.2	Assignment of Study Group	17
7.3	Intervention Group	18
7.4	Delayed Intervention Control	18
7.5	Interaction with Primary Healthcare Providers	18
7.6	Duration of Therapy and Follow-Up	19
8.0	STUDY PROCEDURES.....	20
8.1	Baseline Questionnaire.....	20
8.2	First Home Visit.....	21
8.3	Baseline Counseling Session (Intervention Group).....	21
8.4	Baseline Return of Results (Control Group).....	22
8.5	Handling of Critical Results	22
8.6	Four-month Booster Session	23
8.7	Second Questionnaire and Home Visit	23
8.8	Primary healthcare provider measurements.....	24
8.9	Materials returned to participants and primary healthcare providers	24
8.10	Remote blood pressure monitoring pilot	25

Protocol 8543: Version 7/10/20

9.0	OFF STUDY CRITERIA	26
10.0	ADVERSE EVENTS	26
10.1	Expected Adverse Events.....	26
10.2	Monitoring and Recordings Adverse Events.....	27
11.0	DATA AND SAFETY MONITORING PLAN.....	27
12.0	DATA MANAGEMENT/CONFIDENTIALITY	27
13.0	STATISTICAL CONSIDERATIONS.....	27
13.1	Aim 1 Analytic Plan	28
13.2	Aim 2 Analytic Plan	28
13.3	Aim 3 Analytic Plan	29
13.4	Ethnic and Gender Distribution Chart	32
14.0	REFERENCES.....	33
15.0	APPENDICES	37

1.0 GENERAL INFORMATION

Children and adolescents diagnosed with cancer now have on average >80% 5-year survival. However, premature cardiovascular (CV) disease has become the leading non-cancer cause of late mortality among childhood cancer survivors. Our existing work has shown that traditional CV risk factors such as hypertension, dyslipidemia, insulin resistance/diabetes remain very important, by increasing (in synergistic fashion) the risk of major CV events such as ischemic heart disease and heart failure. However, the existing research has been limited by misclassification of CV risk factor status (i.e., when defined by self-report or medication usage alone), including issues with both underdiagnosis (i.e., people with these risk factors present but who are unaware) and uncertainty of disease control (i.e., potential undertreatment).

This NCI-funded proposal will utilize the largest, best characterized childhood cancer survivor cohort in the world, the Childhood Cancer Survivor Study (CCSS; n=24,466). The CCSS, known to study participants as the “Long Term Follow-Up [LTFU] Study”, is a National Cancer Institute (NCI) funded resource with its data coordination center at St. Jude Children’s Research Hospital and its statistical center at FHCRC.¹ CCSS promotes the development of “ancillary” studies that obtain supplemental funding to extend cohort research beyond what the parent grant can accomplish. Thus, for the proposed CHIIP Study, we will use CCSS-derived validated risk prediction algorithms to select CCSS survivors at high risk of serious heart disease (n~800) based on past cancer treatment exposures. Among these 800 survivors, we propose to determine the magnitude of underdiagnosis and undertreatment of hypertension, dyslipidemia, and diabetes via in-person (home-based) measurements supplemented by medical record review. We predict that around 60% of survivors (n~480) will be underdiagnosed or undertreated with respect to one of these three CV risk factors. *Survivors who are underdiagnosed or undertreated will then be eligible to participate in a 1-year long randomized controlled trial, where we will measure the efficacy of an Institute of Medicine (IOM) recommended personalized survivorship care plan (SCP) emphasizing CV risk, supplemented by a remotely delivered clinician-led self-management counseling intervention, to improve control of these three CV risk factors (i.e., reduce rates of undertreated hypertension, dyslipidemia, and diabetes).* Survivors randomized to the control arm can receive the intervention on a delayed basis. Finally, our proposal seeks to better understand barriers among survivors and their primary healthcare providers that contribute to CV risk factor undertreatment.

Knowledge derived from this study will improve the assessment and treatment of important CV risk factors in this high risk population. The proposed intervention, if successful, will be disseminable and low cost, and will have the potential to improve health and reduce mortality in these younger adults who live the majority of their lives as cancer survivors at increased risk of serious CV disease. The protocol described below is classified as clinical research and will be conducted in compliance with the Fred Hutchinson Cancer Research Center / Cancer Consortium’s approved policies/procedures, and in compliance with all associated Federal regulations.

2.0 INTRODUCTION

2.1 Introduction

There are nearly half a million survivors of childhood cancer estimated to be living in the United States.² Premature CV disease is a leading contributor to late morbidity and mortality in this population.³⁻⁷ Cohort studies from North America and Europe, including the CCSS, have consistently shown that

survivors have a 5+ fold increased risk of serious CV morbidity or mortality vs. the general population, corresponding to ~5% cumulative incidence by age 45 years.³⁻¹¹ Among survivors that have been exposed to cardiotoxic cancer treatments (i.e., anthracyclines and chest radiotherapy), this risk can be markedly greater (Table 1).^{6,7} Demographic characteristics such as age at treatment and gender, and off-target and indirect effects of both radiotherapy and chemotherapy may also affect CV health.^{6,7,12-14}

TABLE 1. Cardiovascular (CV) risk group outcomes among the original CCSS cohort through age 50.

[figure not shown]
Serious CV event	Predicted low risk*		Predicted high risk*	
	No. events / no. at risk	Cumulative incidence / relative risk (RR) vs. siblings	No. events / no. at risk	Cumulative incidence / relative risk (RR) vs. siblings
Ischemic heart disease	73 / 8801	2.3% / RR=2.3, p<0.001	89 / 764	19.9% / RR=17.8, p<0.001
Heart failure	18 / 5197	1.0% / RR=1.8, p=0.11	108 / 2059	12.4% / RR=41.5, p<0.001

*Risk prediction for 5-yr survivors (n=13,060) through age 50, based on sex, diagnosis age, anthracycline and chest radiotherapy doses.^{12,15} Area under the curve [AUC]/C-indices for these models ranged 0.70-0.76 (CCSS), and 0.66-0.82 (external validation cohorts).

Multiple studies in childhood and adult cancer survivors also have shown that even after considering treatment exposures, the presence of conventional CV risk factors such as hypertension, diabetes, and dyslipidemia are important, and may further increase the risk of serious CV disease *in more than additive fashion*.^{7,16,17} Among CCSS participants, hypertension was associated with significantly increased relative excess risks due to interaction [RERI] for ischemic heart disease (after chest radiotherapy) and heart failure (after anthracyclines; Figure 1); RERI was also significantly increased for dyslipidemia and diabetes.⁷ Furthermore, survivors predicted to be at high risk for ischemic heart disease and heart failure, on the basis of their cancer treatment exposures alone, also had higher self-reported rates of hypertension, dyslipidemia, and diabetes vs. survivors predicted to be at low risk (Table 2). Among childhood cancer survivors, the development of these conditions also tends to occur at younger ages compared with siblings or the general population.¹⁸⁻²¹ Given the relatively young age of onset of these conditions that occur more typically in older adults, and the limited knowledge of cancer survivor-specific screening guidelines among general practitioners,^{22,23} most high risk survivors likely do not receive recommended CV screening studies.²⁴⁻²⁶ Thus, there is a compelling rationale to develop interventions for this high risk population designed to target these modifiable CV risk factors.

A frequent limitation of many studies that have examined the relationship between hypertension, dyslipidemia, diabetes, and subsequent more serious outcomes in survivors of childhood cancer, including some of our own work, is reliance on self-report and/or the use of medications as surrogates for these risk factors, in lieu of physiologic or more objective clinical data. Where such data have been available, they often have been collected retrospectively, in a non-standardized fashion, or are only available in cross-sectional analyses with either relatively limited sample sizes, recruited from a single

[figure not shown]
FIGURE 1. Relative risk of serious CV outcomes in CCSS per treatment exposures & hypertension status.⁹

center, and/or a focus on a single cancer type, all of which limit generalizability.^{5,19,20} However, these studies support the hypothesis that underdiagnosis of these CV risk factors is common among survivors.

Also unanswered is the degree to which survivors known to have hypertension, dyslipidemia, or diabetes are adequately treated (undertreatment). We are unaware of studies that have attempted to examine CV risk factor undertreatment among childhood cancer survivors, and such studies are rare among survivors of adult cancers.²⁷⁻³¹ Our prior research showed that survivors with these CV risk factors, defined on the basis of medication use, were at significantly greater risk of more serious CV events (e.g., ischemic heart disease, heart failure) vs. other survivors.^{7,17} Thus, we hypothesize that survivors may be significantly undertreated even when diagnosed. The drivers of undertreatment may be related to healthcare providers not intervening sufficiently and/or non-adherence to appropriate interventions among survivors themselves.^{27,32,33}

TABLE 2. Prevalence of selected CV risk factors by 10-year age groups, stratified by CV-risk status* among the original CCSS cohort (n=13,060) and a sibling comparison group (n=4,023).

The study's intervention will feature an IOM-recommended survivorship care plan [SCP], which is designed to promote knowledge/awareness of personal health risks among survivors and to help disseminate that information to primary healthcare providers.³⁴ Prior research has shown that >80% of adult survivors of childhood cancer are followed by primary care providers,^{25,26,35} and that while the majority of internists and family practitioners report caring for childhood cancer survivors, receipt of a SCP remains uncommon and the vast majority of surveyed providers do not report familiarity with long-

[figure not shown]
term follow-up guidelines for childhood cancer survivors.^{22,23} Our SCP intervention also will be enhanced by the use of recently developed and validated individual CV risk predictors our group has created specifically for childhood cancer survivors (Tables 1, 2). Although the SCP is by itself a tool to foster self-management, we will further supplement it with well-established, focused chronic disease self-management strategies now being applied to improve coordination of cancer survivorship care (Figure 2).³⁶⁻³⁹ Collection of directly measured data also offers an opportunity to further refine risk prediction in the future, beyond using self-report alone (Table 2).

In summary, our proposal will systematically assess the magnitude of underdiagnosis and undertreatment, along with contributing survivor- and provider-specific barriers, among adult-aged CCSS participants predicted to be at high risk of future serious CV disease. Results from this proposal may significantly advance our understanding of CV disease risk among childhood cancer survivors of all ages, *given that many of the cancer treatments CCSS participants received remain in common use today.*^{40,41} If successful, our IOM-based personalized intervention will increase the proportion of survivors and healthcare providers who are aware of current screening guidelines, who receive/deliver more appropriate CV treatment, and who adhere to these guidelines and treatments. The cumulative effect will be a mitigation of survivors' long-term CV risks.

2.2 Clinical Data to Date

The home sampling methodology proposed is based on the NHLBI-supported Women's Health Initiative's (WHI) recently completed Long Life Study, where women (age ≥ 63 years) underwent home-based sample collection using Examination Management Services, Inc. (EMSI). Among 14,000 eligible women, 66% consented, and 85% of those who consented had a biospecimen collected with excellent results ($\geq 95\%$ successful collection). With WHI investigator input, CCSS conducted an EMSI pilot study from Fall 2014 to Spring 2015, approaching 200 randomly selected CCSS participants living within a 50-mile radius of 2 metropolitan areas (Minneapolis & Philadelphia) to complete a home visit featuring a 12-page questionnaire, followed by physical measurements and a fasting blood draw. Participants received a \$50 gift card after study completion and prompt notification (< 72 hours) of any clinically meaningful lab results (standard metabolic panel, lipid profile, hemoglobin [Hb] A1c). After 6 months, 60% of participants had consented (11% active refusals). The median age of participants was 43 years (range 30-57). Among those who consented, 90% completed home-based data collection (all with viable samples, $n=107$) as of April 2015. Although women were more likely to participate than men (58% vs. 42%), participation did not differ significantly by race/ethnicity, age, or treatment era. *Overall,*

FIGURE 2. Survivorship self-management model (adapted from Schulman-Green, McCorkle, and colleagues.⁴⁶

[figure not shown]
the CCSS results approximate those from WHI, despite having a population that is half men, who generally have lower participation rates than women.⁴² Given concerns that more urban CCSS participants may differ from others, we found that those who lived <50 vs. >50 miles from an existing CCSS center (all major metropolitan areas) were similar with respect to demographic and treatment characteristics, except that racial/ethnic minority status was more common among participants residing <50 miles (18% vs. 11%).

Direct measurement of participants from the EMSI pilot study plus data from randomly selected CCSS participants directly measured in 2013 found that abnormal blood pressure, fasting lipid, or blood glucose values were common (median age 42; 45% male). 37% of participants had ≥ 1 value (blood pressures $\geq 140/90$ mmHg, LDL cholesterol ≥ 160 mg/dL or triglyceride ≥ 150 mg/dL, blood glucose ≥ 126 mg/dL or HbA1c $\geq 6.5\%$) meeting commonly accepted clinical standards for therapeutic intervention (*i.e.*, *lifestyle prescription and/or medication management*). This included 23% of survivors who did not have a self-reported history of any of these 3 conditions (*i.e.*, potential underdiagnosis). If thresholds included higher pre-hypertension values ($\geq 130/85$ mmHg) and pre-diabetes (glucose ≥ 100 mg/dL or HbA1c $\geq 5.7\%$), the prevalence of those with an abnormal value increased to 50% (Figure 3). Specifically, among 52 high CV risk survivors, ~60% had an abnormal CV measurement, with the prevalence of individual risk factors ranging 20-40%. Among those with abnormalities, ~40% were undertreated (prevalence of individual undertreated conditions 5-20%) and ~80% had a potentially underdiagnosed condition (prevalence of individual underdiagnosed conditions 15-30%). 20% of survivors also had underdiagnosis of 1 condition and undertreatment of another condition. *These data support our hypotheses that both underdiagnosis and undertreatment of CV risk factors are common among adult-aged survivors of childhood cancer, and that previously published rates based on self-report, particularly if restricted to medication use, underestimate and misclassify the true burden of these risk factors.*

The randomized intervention component of the CHIIP study will be based upon past CCSS intervention studies that incorporated distance-based delivery of SCPs (led by Drs. [name] & [name], both co-investigators).

PROJECT VISION (PI: [name]; Livestrong; 2003-05) enrolled 62 (86% participation rate) adult-aged Hodgkin lymphoma survivors at increased risk for either breast cancer or cardiomyopathy to test the acceptability of an IOM-based SCP supplemented by a study website and an effort to engage participants' primary care providers.⁴³ 92% of participants completed a 6-month post-intervention survey; 75% remembered receiving, reading, and understanding the SCP. Among participants, prior knowledge of mammogram and echocardiogram screening recommendations was low (32% and 12% respectively). During the 6-month study period, 41% and 20% of eligible respondents obtained a mammogram and echocardiogram, respectively, with another 35% (for both tests) planning to do so

FIGURE 3. Yield of directly measured data in relation to self-report among randomly selected CCSS participants (n=175).

*Per self-report. †Among those with self-reported condition if home sampled value was beyond standard therapeutic range. ‡No prior self-reported history of respective condition with abnormal value.

within the next 6 months. As such, these data guide our planned intervention follow-up period of 12 months between assessments. Similar to other studies,⁴⁴ website usage was limited among these young adult survivors (29% visit rate). Primary care providers demonstrated limited engagement: only 19% of providers volunteered to participate; none visited the study website or contacted the study team.⁴³

The ECHOS trial (co-PI: [name]; R01 CA136912; 2009-13) extended the methods in VISION to directly test the efficacy of a SCP supplemented by 2 nurse practitioner-led phone self-management counseling sessions on cardiomyopathy screening (vs. mailed SCP alone).⁴⁵ After 1-year, the randomized intervention group had higher rates of obtaining recommended echocardiograms per self-report validated by medical records (52% vs. 22% SCP alone [$p<0.001$]; RR 2.3, 95% CI 1.7-3.1). The intervention group also was less likely to report lack of physician recommendation as a reason for not obtaining an echocardiogram, suggesting that the counseling further enhanced communication between recipients and their primary care provider beyond what a SCP alone would have accomplished.⁴⁶ The study had an 87% retention rate at 1-year follow-up (n=411 of 472).⁴⁵

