3.4 Estimated Accrual

The proposal would seek to enroll up to 800 participants to answer Primary Aim 1. If 60% of those participants are found to have an abnormal CV condition, up to 480 would then be eligible to participate in the randomized controlled trial as part of Primary Aims 2 and 3 (n=240 in each study arm).

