9.0 OFF STUDY CRITERIA

This would occur if:

- A participant withdrew consent for any further data submission, or
- The participant was unable to complete the initial home visit procedures (e.g., unsuccessful blood draw), or
- Once a participant has completed all study assessments.

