Potential pitfalls / solutions: Our EMSI pilot achieved 60% enrollment. Funding from this proposal will enhance recruitment rates by providing an upfront (rather than conditional) participation incentive, which has been associated with higher rates of study participation.^{62,63} We will closely examine the demographic characteristics, past cancer treatment exposures, and self-reported burden of CV and other chronic conditions of survivors who are approached vs. not approached, and who ultimately participate vs. not. If differences are found, we will apply inverse probability weighting as a way to assess the sensitivity of our estimates.

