Secondary analyses: In case survivors who were newly diagnosed (i.e., underdiagnosed) following their 1st home visit differ in their response to the intervention vs. those previously diagnosed but undertreated, we will examine estimates stratified by diagnosis status at the 1st home visit. For similar reasons, we also will examine estimates if pre-diabetes are excluded. In our primary model, we also will explore whether differences vary by sex, current age, time since cancer diagnosis, obese (BMI ≥ 30 kg/m²) vs. not, health insurance vs. not, and recent history of being seen in a dedicated long-term follow-up clinic for survivors vs. not. We also will explore, among intervention participants, whether action plan scores from the 4-month session are associated with differential undertreatment rates (as a single parameter). Finally, we plan to also compare across the study arms, the measured CV risk factor values from the 2nd home visit separately: 1) average systolic pressure, 2) average diastolic pressure, 3) LDL, 4) triglyceride, 5) blood glucose, and 6) HbA1c. For this subanalysis we will use linear models, adjusting for the value at the 1st home visit as a covariate.

Sample size considerations: Assuming 60% of Aim 1 participants (n=800) meet Aim 2 eligibility with a subsequent conservative 20% drop-out rate, ~380 survivors (190/arm) would have complete data. The study would be 80% powered ($\alpha=0.05$) to detect RRs ≤ 0.88 (i.e., $\geq 12\%$ reduction in the intervention vs. control group) if the prevalence of having an undertreated CV risk factor among controls after the 2nd home visit was 90% (10% reduction from baseline). If controls had an unlikely 50% reduction, we can still detect RRs ≤ 0.71 . Analyses stratified by initial underdiagnosis or undertreatment status (~75-150/arm) will be able to detect RRs ≤ 0.79 to ≤ 0.86 , respectively. Systematic reviews have reported RRs 0.6-0.8 for strategies similar our proposed interventions in the general population.^{64,65} For continuous outcomes (secondary analyses), we will be powered to detect change equaling $\sim 30\%$ of 1 standard deviation, which equates to 5 mmHg systolic blood pressure, 3 mmHg diastolic pressure, 10 mg/dL LDL, 30 mg/dL triglyceride, 10 mg/dL glucose, and 0.3% HbA1c. Differences within these ranges have been reported by others for interventions conducted in the general population.⁶⁶⁻⁶⁸

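### The plan uses 800 both as survivors enrolled and as survivors with a completed 1st home visit; if it means enrolled, the pilot's 90% completion turns 190/arm and 80% power into about 173/arm and 75–76%.

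*Combined protocol and SAP*

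**What the plan says.** **The enrollment figure.** Section 3.4 states: "The proposal would seek to enroll up to 800 participants to answer Primary Aim 1". The accrual chart in 13.4 gives 800 as the planned enrollment total. Table 3 times the 1st home visit from enrollment (within 2 months, at most 6), so enrollment comes before the visit. Section 13.1 says "Our EMSI pilot achieved 60% enrollment", and section 2.2 reports that same 60% as the share of pilot participants who consented. Enrollment in this plan therefore means consent.

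**The measured figure.** Table 9 in 13.1 gives the precision of the Aim 1 prevalences at N=800. Section 3.1.1 expects about 480 of the 800 to have an abnormal value at the initial home visit. The Aim 2 sample size in 13.2 begins: "Assuming 60% of Aim 1 participants (n=800) meet Aim 2 eligibility with a subsequent conservative 20% drop-out rate". It concludes that about 380 "survivors (190/arm) would have complete data".

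**What happens between the two.** On the pilot, section 2.2 says: "Among those who consented, 90% completed home-based data collection" (107 people, as of April 2015). Section 9.0 lists as a reason for going off study: "The participant was unable to complete the initial home visit procedures (e.g., unsuccessful blood draw"). Section 8.2 likewise ends participation when the lipid, glucose and HbA1c samples cannot be obtained.

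**The concern.** The same 800 stands at two points in the participant flow that are separated by a step where people are lost. Someone who consents but does not complete the 1st visit has no Aim 1 result and cannot be randomized. Going from 800 enrolled to 800 measured without a factor assumes that everyone completes the visit, and the plan's own pilot did not show that.

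Nothing else in the plan absorbs the loss. The 20% drop-out is described as subsequent to eligibility. The pitfalls paragraph in 13.1 deals with the enrollment rate, and the one in 13.2 with the rate of abnormal findings. Neither mentions visit completion.

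At stake are the stated Aim 2 size (480 randomized, about 380 with data), the stated 80% power and, to a small extent, the precision in Table 9.

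**Working it through.** **Inputs**
- Enrolled: 800 (3.4, 13.4).
- Eligible for Aim 2: 60%. Later drop-out: 20%. Allocation 1:1 (13.2, 7.2).
- Control prevalence and RR: 90% with 0.88, and 50% with 0.71; alpha 0.05 (13.2).
- Completion of the 1st visit among consenters: 90% (2.2). Check: 60% of 200 approached = 120 consented, and 107/120 = 89.2%.

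**1. The plan's size.** 800 × 0.60 = 480. 480 × 0.80 = 384, or 192/arm, which the plan rounds to about 380 and 190/arm.

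**2. The plan's power.** Section 13.2 does not name the test. Table 9 uses Fisher's exact test, so I computed its two-sided power by full enumeration. Intervention prevalences are 0.90 × 0.88 = 0.792 and 0.50 × 0.71 = 0.355.
- 190/arm, 0.90 vs 0.792: 80.5%.
- 190/arm, 0.50 vs 0.355: 79.5%.

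Both match the stated 80%. A continuity-corrected normal approximation gives 79.5% for the first and also fits. The uncorrected pooled approximation gives 83.3% and does not.

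**3. With the 1st-visit step included.** Measured: 800 × 0.90 = 720. Eligible: 720 × 0.60 = 432. Complete data: 432 × 0.80 = 345.6, about 346, or 173/arm.

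| Scenario | 190/arm | 173/arm |
|---|---|---|
| Power, RR 0.88, control 90% | 80.5% | 76.5% |
| Power, RR 0.71, control 50% | 79.5% | 74.6% |
| RR detectable at 80% power, control 90% | 0.88 | 0.874 |
| RR detectable at 80% power, control 50% | 0.71 | 0.692 |

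The continuity-corrected figure for RR 0.88 at 173/arm is 75.2%.

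**4. Table 9 at 720.** Half-width = 1.96 × √(p(1 − p)/N).

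| Prevalence | N=800 | N=720 |
|---|---|---|
| 5% | 1.5 | 1.6 |
| 20% | 2.8 | 2.9 |
| 50% | 3.5 | 3.7 |

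(percentage points)

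**5. The other reading.** If 800 is the number of completed visits, steps 1 and 2 stand as printed, and the number to enroll is 800/0.90 = 889.

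**6. Sensitivity to the assumptions**
- 90% completion with 87% retention in place of 80%: 800 × 0.90 × 0.60 × 0.87 = 376, or 188/arm. Power is 80.0% at RR 0.88.
- 85% completion (the share of consenters with a biospecimen in the Women's Health Initiative study, 2.2) with 20% drop-out: 800 × 0.85 × 0.60 × 0.80 = 326, or 163/arm. Power is 73.5% at RR 0.88.
- Eligibility needed to recover 480 from 720 measured: 480/720 = 66.7%.

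**The case against.** **800 may mean measured survivors.** Table 9, section 3.1.1 and the wording of 13.2 all treat it so, and on that reading the power is right. This stands, and it is why the point is conditional. It does not remove the inconsistency, because 3.4 and 13.4 would then give the wrong enrollment target.

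**The 90% is soft.** It is a status as of April 2015 from two metropolitan areas, and the text does not say whether the remaining 10% had dropped out or were still pending. The pilot required fasting and paid on completion. This trial requires no fasting, pays up front, offers rescheduling and allows up to 6 months. Completion could be better, so 90% is a planning value and not an established yield.

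**Other inputs may err the other way.** The 60% rests on 52 high-risk pilot survivors; for 31 of 52 the exact 95% interval is about 45% to 73%, which includes the 66.7% that would restore 480. The blood pressure threshold for eligibility (130/80) is also broader than the 130/85 in the wider pilot definition. On retention, the earlier care-plan trial did better than 80%: "The study had an 87% retention rate at 1-year follow-up (n=411 of 472"). At 87%, the loss at the 1st visit is almost fully absorbed. This stands as a caveat, but as written the drop-out allowance does not cover loss before eligibility.

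**The effect is small.** At RR 0.80, the weak end of the range that 13.2 cites, power at 173/arm with control prevalence 90% is still 98.9%.

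**A stronger reading to avoid.** A reader might multiply 87% by 90%, get 78% retention, and conclude that 20% drop-out is not conservative and should be 22%. The documents do not support that. It applies a first-visit completion rate to people who have already completed such a visit. It also ignores the second-visit fallbacks in 8.7 (dried blood spot, fully remote assessment) and the absence of a maximum window in Table 3.

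**Conclusion.** The plan's figures for enrollment and for measured survivors cannot both be 800 once its own pilot completion rate is applied. If 800 is enrollment, the size that follows is about 173/arm, and power is about 76% at RR 0.88 and 75% at RR 0.71, a shortfall of 4 to 5 points. If 800 is completed visits, the power is sound and the enrollment target is about 89 too low. The wording of 3.4, 13.4 and Table 3 favours the first reading but does not settle it.

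This rests on 90% completion carrying over from the pilot, on the plan's 60% and 20% unchanged, and on Fisher's exact test, which reproduces the stated figures. All the power figures are for one binary outcome per person, as in the plan's own calculation. They are not the power of the planned GEE analysis on up to three outcomes. Nor do they show that the trial will be underpowered, since better completion, eligibility or retention could each make up the difference.

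**What to change.** State in 3.4 and 13.2 whether 800 counts enrolled survivors or completed 1st home visits.

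- **If enrolled:** restate about 720 with an Aim 1 result, 432 eligible and 346 with complete data (173/arm), with 80% power for RR ≤0.87 (control 90%) and ≤0.69 (control 50%). Restate the N=800 precision column of Table 9 at N=720, with half-widths of 1.6, 2.9 and 3.7 points. Carry the smaller eligible number into the other sections that quote 480 or 240 per arm.
- **If completed visits:** keep the power figures and change the enrollment figure in 3.4 and the total in 13.4 to about 889.

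In either case, label the 90% as an assumption from the pilot, and note that 87% retention would bring the size back to about 188/arm and 80% power at RR 0.88. The description of the 20% drop-out can stay.

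The first option costs wording and figures only, with slightly less favourable stated power. The second means enrolling about 89 more survivors than the stated target.
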